4.2.8.4 Laboratory Data

All reported clinical laboratory test results will be assigned to one of the time points using the time windows specified in the Table 3. All will be performed for the SP by treatment regimen and cirrhosis status.

Changes from baseline to each post-baseline visit will be summarized descriptively (N, mean, SD, median, minimum, maximum). A summary table will show laboratory hematology. In another table, information about clinical chemistry will be summarized.

In a further table CD4 and HIV-RNA are displayed for patients with HIV only by visit.

Instead of the shift tables mentioned in the study protocol, the number and percentage of subjects with post-baseline values until EoT meeting the specified criteria for Potentially Clinically Significant (PCS) laboratory values (defined in Table 2) will be summarized. A post-baseline value must be more extreme than the baseline value to be considered a PCS finding.

Table 9 Criteria for PCS laboratory values

Laboratory data	Very Low	Very High
Laboratory hematology		
Hemoglobin [g/L]	<80	
Platelets [10^9 /L]	<50	
Laboratory clinical chemistry		
ALT		>5 x ULN and >= 2 x baseline
AST		>5 x ULN and >= 2 x baseline
Creatinine [$\mu\text{mol}/\text{L}$]		>132.605
Creatinine clearance [mL/min]***	<50	

*** estimated by Cockcroft-Gault-Formula (see above)

Additionally, for hemoglobin and creatinine clearance, the number and percentage of subjects with a maximum Common Terminology Criteria for Adverse Events (CTCAE) Grade of 0, 1, 2, 3, or 4 (see definitions in Table 10) at any post-baseline visit (regardless of the baseline value) through the end of treatment (i.e., Final Treatment Value) will be summarized. For the liver function tests (LFTs) of ALT and AST, the number and percentage of subjects in with a maximum CTCAE Grade of 0, 1, 2, 3, or 4 (see definitions in Table 10) at any post-nadir visit through the end of treatment (i.e., Final Treatment Value) will be summarized. Note, for these analyses, the nadir is used for reference (including baseline).

Table 10 Definition of CTCAE Grades 0-4

Laboratory data	Grade 0	Grade 1	Grade 2	Grade 3	Grade 4
ALT	<=ULN	>ULN – 3 x ULN	> 3 – 5 x ULN	> 5 – 20 x ULN	> 20 x ULN
AST	<=ULN	>ULN – 3 x ULN	> 3 – 5 x ULN	> 5 – 20 x ULN	> 20 x ULN
Hemoglobin Decreased [g/L]	>=130	<130 – 100	< 100 - 80	< 80 - 65	< 65
Creatinine Clearance [mL/min]	>= 75	< 75 - 60	< 60 - 30	< 30 – 15	< 15

Table 11 Overview of Outputs for Safety Variables

Output Title	Output Short Name	Analysis Population
Exposure to Study Medication by Treatment Regimen and Cirrhosis Status - SP - <country>	tesm_<c>_tc_sp	Safety population
Unintended Medication Error/ Pregnancy by Treatment Regimen and Cirrhosis Status -- SP - <country>	tum_<c>_tc_sp	Safety population
Treatment-emergent AEs by Treatment Regimen and Cirrhosis Status - SP - <country>	tae_<c>_tc_sp	Safety population
Serious Treatment-emergent AEs by Treatment Regimen and Cirrhosis Status - SP - <country>	tsae_<c>_tc_sp	Safety population
Non-Serious Treatment-emergent AEs by Treatment Regimen and Cirrhosis Status - SP - <country>	tnsae_<c>_tc_sp	Safety population
Treatment-emergent AEs by Severity by Treatment Regimen and Cirrhosis Status - SP - <country>	taes_<c>_tc_sp	Safety population
Treatment-emergent AEs Leading to Death by Treatment Regimen and Cirrhosis Status - SP - <country>	taed_<c>_tc_sp	Safety population
Treatment-emergent AEs Leading to Hospitalization by Treatment Regimen and Cirrhosis Status - SP - <country>	taeh_<c>_tc_sp	Safety population
Treatment-emergent AEs Possibly Related to ABBVIE Regimen by Treatment Regimen and Cirrhosis Status - SP - <country>	taera_<c>_tc_sp	Safety population
Treatment-emergent AEs Possibly Related to Ribavirin in Patients taking RBV by Treatment Regimen and Cirrhosis Status - SP - <country>	taerr_<c>_tc_sp_RB V	Safety population: patients taking RBV
Treatment-emergent AEs Caused by Medication Error - Paritaprevir/r-Ombitasvir - by Treatment Regimen and Cirrhosis Status - SP - <country>	taempo_<c>_tc_sp	Safety population
Treatment-emergent AEs Caused by Medication Error - Dasabuvir - in Patients taking 3DAA by Treatment Regimen and Cirrhosis Status - SP - <country>	taemd_<c>_tc_sp_3d aa	Safety population: patients taking 3DAA
Treatment-emergent AEs Leading to Withdrawal of ABBVIE Regimen by Treatment Regimen and Cirrhosis Status - SP - <country>	taewa_<c>_tc_sp	Safety population
Treatment-emergent AEs Leading to Withdrawal of Ribavirin in Patients taking RBV by Treatment Regimen and Cirrhosis Status - SP - <country>	taewr_<c>_tc_sp_RB V	Safety population: patients taking RBV
Listing of SAEs - SP - <country>	lsae_<c>_sp	Safety population
Glossary for AEs - <country>	tgae_<c>	-
Co-medication by Treatment Regimen and Cirrhosis Status - SP - <country>	tcom_<c>_tc_sp	Safety population
Co-medication by Profile and by Treatment Regimen and Cirrhosis Status - SP - <country>	tcomp_<c>_tc_sp	Safety population
Associated Treated Condition by Treatment Regimen and Cirrhosis Status - SP - <country>	tatc_<c>_tc_sp	Safety population
Associated Treatment Profiles by Medication of Special Interest and by Treatment Regimen and Cirrhosis Status - SP - <country>	tatp_<c>_mtc_sp	Safety population

Herbals Except St. John's Wort, Homeopathics or Other Drugs Taken During Study by Treatment Regimen and Cirrhosis Status - SP - <country> Glossary for Co-medication - <country>	theho_<c>_tc_sp	Safety population
Laboratory Hematology by Treatment Regimen and Cirrhosis Status - SP - <country>	tgcom_<c>	-
Laboratory Clinical Chemistry by Treatment Regimen and Cirrhosis Status - SP - <country>	tlh_<c>_tc_sp	Safety population
CD4 and HIV RNA in Patients With HIV by Treatment Regimen and Cirrhosis Status - SP - <country>	tlc_<c>_tc_sp	Safety population
Potentially Clinically Significant Laboratory Values by Treatment Regimen and Cirrhosis Status - SP - <country>	tlch_<c>_tc_sp_hiv	Safety population
Worst Laboratory Values by Treatment Regimen and Cirrhosis Status - SP - <country>	tpcs_<c>_tc_sp	Safety population
	twlv_<c>_tc_sp	Safety population

The layouts of the tables mentioned above are provided in Part II of the SAP (Table Shells).

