The ABBVIE REGIMEN has been studied with and without RBV in over 2,300 patients in Phase III trials across a variety of patient populations including those with compensated cirrhosis. Based on Phase III data, the ABBVIE REGIMEN, with or without RBV, was well tolerated with a low discontinuation rate. Adverse events (AEs) were typically mild, and many of the AEs and laboratory abnormalities reported were attributable to the presence of RBV. However, these AEs were much milder than observed when RBV was given in combination with interferon. Transient, asymptomatic serum alanine aminotransferase (ALT) elevations were observed at a low rate, were not associated with hepatic dysfunction and generally resolved with ongoing treatment. A disproportionate number of the cases were in women on concurrent ethinyl estradiol-containing therapy (i.e., contraceptives or hormone replacement) and discontinuation of the hormonal therapy with continuation or brief interruption of the ABBVIE REGIMEN led to resolution in serum ALT elevation. Transient elevations in serum bilirubin (predominantly indirect) were observed in subjects receiving the ABBVIE REGIMEN with RBV, related to the inhibition of the bilirubin transporters, organic anion-transporting polypeptides (OATPs) 1B1/1B3, by paritaprevir and RBV-induced hemolysis. Bilirubin elevations occurred after initiation of treatment, peaked by study Week 1, and generally resolved with ongoing therapy.

---

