**Table 4 - Analysis Time Windows**

Phase	Time point	Time Window
Pre-Treatment	Baseline	Last value prior to start of study treatment (i.e. $\leq$ study day 1)
Treatment Weeks	4 (day 29)	Study day during treatment period (Study day 1 = first treatment day)
	8 (day 57)	15 - 42
	12 (day 85)	43 - 70
	16 (day 113)	71 - 98
EoT	Actual EoT	99 - 126
		Study day of last dose (28 days prior to EoT - 7 days post EoT)
Post Treatment	4 weeks (28 days post EoT)	8 – 56 post EoT
	12 weeks (84 days post EoT)	57 – 126 post EoT
	24 weeks (168 days post EoT)	127 – 252 post EoT

Mean changes from baseline to each post-baseline visit will be summarized descriptively.

---

Confidential Information

Laboratory data values collected during the treatment period will be categorized as low, normal, or high based on reference ranges used in this study. The number and percent of patients who experience post-baseline shifts during treatment in clinical laboratory values from low/normal to high and high/normal to low based on the reference range will be summarized.

Additional details of the analyses of clinical laboratory data will be specified in the SAP.

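### The SAP's replacement for the protocol's laboratory shift tables omits total bilirubin, so no laboratory-based count of patients with raised on-treatment bilirubin is produced

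*SAP*

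**What the plan says.** **Protocol 9.7.4** classifies on-treatment laboratory values as low, normal or high against the reference range and plans a patient count: "The number and percent of patients who experience post-baseline shifts during treatment in clinical laboratory values from low/normal to high", and likewise for downward shifts. No analyte is excluded. Further laboratory detail is left to the SAP. Protocol 9.4.1.1 to 9.4.1.3 list total bilirubin as key clinical chemistry at baseline, on treatment and post-treatment, to the extent that routine practice supplies it.

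**Protocol 7.1** describes the effect: "Transient elevations in serum bilirubin (predominantly indirect) were observed in subjects receiving the ABBVIE REGIMEN with RBV". It attributes this to transporter inhibition by paritaprevir and to ribavirin haemolysis. It puts the peak by Week 1, says the rises generally resolved on continued therapy, reports a lower frequency without ribavirin, and says the rises were not associated with aminotransferase elevations.

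**SAP 4.2.8.4** declares the substitution: "Instead of the shift tables mentioned in the study protocol, the number and percentage of subjects with post-baseline values until EoT" that meet PCS criteria are summarized. Table 9, "Criteria for PCS laboratory values", lists haemoglobin, platelets, ALT, AST, creatinine and creatinine clearance. The grade counts in Table 10 are limited in the same way: "for hemoglobin and creatinine clearance, the number and percentage of subjects with a maximum Common Terminology Criteria for Adverse Events (CTCAE) Grade", and "For the liver function tests (LFTs) of ALT and AST, the number and percentage of subjects". What remains for bilirubin is this: "Changes from baseline to each post-baseline visit will be summarized descriptively", with N, mean, SD, median, minimum and maximum.

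**The concern.** Describing tolerability is a secondary objective (Protocol 8.2.2). For a laboratory effect that the protocol itself attributes to the regimen, the natural output is how many patients went above a stated level. The protocol planned a count of that kind. The SAP removes it without giving a reason, and its replacement covers the other main safety analytes but not this one.

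Two things are lost. First, the report cannot say from laboratory data how many patients had raised bilirubin on treatment. Second, ALT and AST elevations are counted but cannot be set beside bilirubin in the same patients. The protocol's background statement that the two were not associated therefore cannot be checked at patient level.

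**Working it through.** The plan gives no figure to reproduce here, so the check sets its lists side by side.

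**1. Analytes documented on treatment (Protocol 9.4.1.2) against the SAP patient counts**

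| Analyte | Table 9 (PCS) | Table 10 (CTCAE) |
|---|---|---|
| Haemoglobin | yes | yes |
| Platelets | yes | no |
| ALT | yes | yes |
| AST | yes | yes |
| Creatinine / creatinine clearance | yes / yes | no / yes |
| Total bilirubin | **no** | **no** |
| Gamma-GT | **no** | **no** |

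Bilirubin and gamma-GT are the two analytes without a laboratory-based count. The protocol names only bilirubin as showing an effect of the regimen.

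**2. Can the by-visit change summary show the peak?**

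SAP Table 3 gives on-treatment windows of days 15–42, 43–70 and 71–98, and an EoT window from 28 days before to 7 days after the last dose. For a 12-week course with the last dose assumed on day 84, the EoT window runs from 84 − 28 = 56 to 84 + 7 = 91. The windows together cover days 15 onward, so days 2–14 (13 days) fall in none. A value drawn at the stated Week 1 peak would not enter the by-visit summary. The PCS rule takes any post-baseline value until EoT, so a PCS count would include that value if it was measured.

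**3. Other outputs that could reveal raised bilirubin**

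- Treatment-emergent adverse events by preferred term (SAP 4.2.8.3): an abnormal laboratory finding can be an adverse event (Protocol 11.1.1), but it is counted only if the site reports it. The separate non-serious table also shows only terms reaching 5% in a treatment group.
- Jaundice and dark brown urine among treated symptoms (SAP 4.2.7.2.3): only symptoms treated at a consultation or in hospital.
- Hyperbilirubinaemia as a sign of decompensation (SAP 4.2.6.2): a baseline item.

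None is a count of on-treatment laboratory values.

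**4. What a restored count would report**

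The documents give no bilirubin rate, so the event counts below are assumed. The denominators are the two ends of the expected enrolment (50–55) and assume every patient has a post-baseline value. The Wilson 95% limits are

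[p + z²/(2n) ± z·√(p(1 − p)/n + z²/(4n²))] / (1 + z²/n), with z = 1.96.

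Example, 3 of 50: p = 0.06; centre (0.06 + 0.0384)/1.0768 = 0.0914; half-width 1.96 × √(0.001128 + 0.000384)/1.0768 = 0.0708; limits 2.1% to 16.2%.

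| Patients with raised bilirubin | n = 50 | n = 55 |
|---|---|---|
| 0 | 0% (0.0–7.1) | 0% (0.0–6.5) |
| 1 | 2.0% (0.4–10.5) | 1.8% (0.3–9.6) |
| 3 | 6.0% (2.1–16.2) | 5.5% (1.9–14.9) |
| 5 | 10.0% (4.3–21.4) | 9.1% (3.9–19.6) |
| 10 | 20.0% (11.2–33.0) | 18.2% (10.2–30.3) |

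The intervals are wide, but the count is informative. Even zero cases would give an upper limit near 7%.

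**The case against.** The strongest reply has four parts.

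- **The change is open and permitted.** The SAP says that it departs from the protocol, and the protocol defers laboratory detail to the SAP. This stands: nothing is concealed, and the issue is only the missing analyte.
- **Raised bilirubin is not invisible.** A reader might infer that bilirubin is left with means alone, or that no table counts affected patients at all. The documents support neither. The change summary includes the maximum, which shows the largest rise per group and visit window, and reported or treated cases appear in the adverse event and resource-use tables. But a maximum does not say how many patients rose or to what level, and those tables depend on reporting or treatment.
- **The protocol's shift table was not assured for bilirubin.** The upper limit of normal is explicitly requested only for ALT and AST, and a low/normal-to-high shift does not separate marginal from marked rises. Both points stand. A reader might also infer that the protocol promised a bilirubin count in each of the 20 safety-population groups. It did not: those groups are defined in the SAP, and Protocol 9.7.4 names no strata for the shifts.
- **The effect is described as benign, and measurement is opportunistic.** The protocol calls the rises transient and generally resolving, and bilirubin is available only where routine practice measured it. A reader might infer an unexamined liver injury signal, or collection at every visit. The documents support neither. This limits the importance of the point but does not explain why the other main safety analytes are counted and this one is not.

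**Conclusion.** The point holds for laboratory-based, on-treatment counts. SAP 4.2.8.4 drops a protocol-planned type of patient count, and its replacement leaves out a laboratory effect that the protocol attributes to the regimen, mainly with ribavirin. The remaining change summaries can miss the stated Week 1 peak, because days 2–14 belong to no window in a 12-week course. The other outputs see only reported or treated cases.

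The consequence is confined to the descriptive tolerability objective; the SVR12 analysis is unaffected. The number of patients missed cannot be estimated, since the documents give neither a bilirubin event rate nor the frequency of Week 1 sampling. The window calculation assumes a last dose on day 84; in a patient who stops very early, the EoT window would reach back into days 2–14. The SAP's table shells (Part II) were not available, but the SAP text itself defines the PCS and CTCAE contents without bilirubin. The change should be made because it is specific and costs almost nothing.

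**What to change.** Add a total bilirubin row to SAP Table 9 with pre-specified absolute reporting cut-offs, as that table already does for haemoglobin, platelets and creatinine. This avoids the need for a local upper limit of normal. The boundaries printed in Protocol Annex 4 (34.2 and 51.3 µmol/L) are available for this. They are Child-Pugh boundaries, so they should be labelled as descriptive reporting cut-offs, not as CTCAE grades or clinical action limits. For the same reason the row does not belong in Table 10.

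Apply the existing PCS rules: any post-baseline value until EoT, counted only if more extreme than baseline. Report the number of patients with a post-baseline bilirubin value and use it as the denominator. List any patient who also meets the ALT PCS criterion, with dates, so that the two can be read together.

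In the same edit, correct the SAP's pointer for the PCS criteria, which cites Table 2 although they are in Table 9.

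The cost is one table row and a short listing from data already planned for the eCRF. The limit is that patients whose bilirubin was not measured near the peak will still be missed.

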4.2.6.5 CHC related and other laboratory data at baseline

The laboratory data at baseline are the most recent available data prior to first administration of the ABBVIE REGIMEN (including day 1, see Table 3). All reported clinical laboratory test results will be assigned to one of the time points using the time windows specified in the Table 3.

A summary table will show CHC related laboratory data at baseline, i.e. HCV RNA in IU/mL, HCV RNA in log₁₀ IU/mL, and HCV RNA categorized using 400,000, 800,000, 6,000,000 and

10,000,000 as cut-offs, ALT, ALT ratio, AST, AST ratio, APRI, FIB-4. ALT-ratio, AST ratio, APRI and FIB-4 will be calculated as follows:

ALT ratio = ALT value / upper limit of normal (ULN) of local laboratory

AST ratio = AST value / ULN of local laboratory

APRI = $100 \times \text{AST} [\text{IU/L}] / (\text{ULN of AST} [\text{IU/L}] * \text{Platelets} [10^9/\text{L}])$ (APRI= aspartate aminotransferase to platelet ratio index [1]; calculated, if laboratory assessments took place within 30 days)

FIB-4 = $(\text{Age} [\text{years}] \times \text{AST} [\text{IU/L}]) / (\text{Platelets} [10^9/\text{L}] * \text{Square root of ALT} [\text{IU/L}])$ (FIB-4= Fibrosis 4 index [2]; calculated, if laboratory assessments took place within 30 days)

In addition the following other key laboratory data at baseline will be summarized: γ-GT, total bilirubin, albumin, creatinine, creatinine clearance (continuous and categorize as Grade 1 [60-<LLN mL/min], Grade 2 [30-<60 mL/min], Grade 3 [15-<30 mL/min], Grade 4 [<15 mL/min]; if LLN is missing 75 mL/min is used), AFP, hemoglobin, platelets, prothrombin time, and INR (if documented instead of prothrombin time). The creatinine clearance will be calculated as follows:

Creatinine clearance [ml/min] = $(140-\text{age}) * \text{Weight} (\text{in kg}) * \text{constant} / \text{Creatinine} (\text{in } \mu\text{mol/L})$ (constant is 1.23 for men and 1.04 for women; calculated by Cockcroft-Gault-Formula)

A further table CD4 and HIV-RNA test results are displayed for patients with HIV only.

Table 6 Overview of Outputs for Baseline Characteristics

Output Title	Output Short Name	Analysis Population
Socio-demographic Characteristics by Genotype and Cirrhosis Status - CP - <country>	tdm_<c>_gc_cp	Core population
Socio-demographic Characteristics by Genotype and Cirrhosis Status - TP - <country>	tdm_<c>_gc_tp	Target population

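### Worst on-treatment hemoglobin and creatinine-clearance grades ignore baseline, and with the shift tables dropped no patient count shows who worsened within the Grade 1–2 range above the PCS limits

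*SAP*

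**What the plan says.** Protocol 9.7.4 planned to report the number and percentage of patients with "post-baseline shifts during treatment in clinical laboratory values from low/normal to high and high/normal to low", judged against reference ranges.

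SAP 4.2.8.4 states that PCS counts take the place of those shift tables. The PCS limits in Table 9 include hemoglobin below 80 g/L and creatinine clearance below 50 mL/min, with the condition "A post-baseline value must be more extreme than the baseline value to be considered a PCS finding".

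The same section then adds a worst-grade table. For hemoglobin and creatinine clearance the maximum grade is taken "at any post-baseline visit (regardless of the baseline value) through the end of treatment". For ALT and AST the grade is instead taken after the nadir, with baseline included in the nadir. Table 10 uses one fixed set of limits:

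- Hemoglobin (row "Hemoglobin Decreased [g/L]"): Grade 0 is 130 g/L or more, Grade 1 is below 130 to 100, Grade 2 is below 100 to 80.
- Creatinine clearance: Grade 0 is 75 mL/min or more, Grade 1 is below 75 to 60, Grade 2 is below 60 to 30.

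At baseline, SAP 4.2.6.5 grades creatinine clearance as "Grade 1 [60-<LLN mL/min], Grade 2 [30-<60 mL/min], Grade 3 [15-<30 mL/min], Grade 4 [<15 mL/min]", and "if LLN is missing 75 mL/min is used". Hemoglobin appears there only in a list ("AFP, hemoglobin, platelets, prothrombin time, and INR (if documented instead of prothrombin time)"), without grades.

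SAP 4.2.8.4 also summarizes change from baseline at each visit by N, mean, SD, median, minimum and maximum.

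**The concern.** A worst-grade table that ignores baseline mixes two things: what the patient brought into the study and what happened on treatment. The SAP's neighboring counts avoid this. PCS values must be worse than baseline, ALT and AST grades are referenced to the nadir, and treatment-emergent adverse events must in general begin or worsen after the drug starts. Hemoglobin and creatinine-clearance grades are the exception, and no reason is given.

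The mixture matters because Protocol 7.1 attributes many laboratory abnormalities to ribavirin and names ribavirin-induced hemolysis, and describing tolerability is a stated objective. The table is laid out by regimen (with or without ribavirin) and cirrhosis status. Under the label-based core-population rules in SAP 4.2.1, ribavirin use goes with genotype and cirrhosis, so the strata may well differ at baseline. A difference between strata in Grade 1–2 counts could then reflect who is in the stratum as well as the drug. With 50–55 patients spread over 20 overlapping safety groups, a few pre-existing low values move a stratum's percentage visibly.

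**Working it through.** The plan states no rate or precision for this analysis, so there is no figure to reproduce. The check applies the written rules to example patients and then gives a scale under stated assumptions.

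**Step 1. The rules applied.** Inputs are the Table 10 grades and the Table 9 PCS limits with the worse-than-baseline condition. The patient values are illustrations. The last column applies the Table 10 limits at both times.

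| Variable | Baseline → worst on treatment | Grade counted | PCS finding | Change | Grade worsened? |
|---|---|---|---|---|---|
| Hb, g/L | 125 → 125 | 1 | no | 0 | no |
| Hb | 95 → 95 | 2 | no | 0 | no |
| Hb | 95 → 110 | 1 | no | +15 | no (improved from 2) |
| Hb | 170 → 131 | 0 | no | −39 | no |
| Hb | 129 → 100 | 1 | no | −29 | no |
| Hb | 130 → 129 | 1 | no | −1 | yes |
| CrCl, mL/min | 45 → 45 | 2 | no | 0 | no |
| CrCl | 59 → 31 | 2 | yes | −28 | no |
| CrCl | 95 → 76 | 0 | no | −19 | no |

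Stable and improving patients are counted at Grade 1 or 2.

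**Step 2. The gap.** An on-treatment grade of 1 or more starts below 130 g/L or 75 mL/min. The PCS count, which is baseline-referenced, starts below 80 g/L or 50 mL/min. Between the two, at hemoglobin 80–129 g/L and clearance 50–74 mL/min, patients are counted only without reference to baseline.

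**Step 3. Scale for hemoglobin (assumed distributions).** The share of single values below 130 with no drug effect is Φ((130 − mean)/SD).

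- Mean 150, SD 12: Φ(−1.67) = 4.8%. Times 50 is 2.4 patients; times 55 is 2.6.
- Mean 135, SD 15: Φ(−0.33) = 36.9%. Times 50 is 18.5 patients; times 55 is 20.3.

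**Step 4. What a worsening count does.** This is a simulation with no drug effect. Each patient has an underlying level drawn with the mean and SD shown, one baseline value and three on-treatment values, and a within-patient SD of 5 g/L. All of these are assumptions.

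| Mean, SD (g/L) | Worst grade ≥1 | Grade worsened from baseline |
|---|---|---|
| 135, 12 | 47.5% | 15.8% |
| 140, 15 | 35.3% | 11.9% |
| 145, 15 | 24.3% | 9.2% |
| 150, 12 | 10.5% | 5.5% |

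The remainder is visit-to-visit noise, so the worsening count reduces the problem without removing it.

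**Step 5. The clearance limit at the two times.** With an LLN of 75 or a missing LLN, SAP 4.2.6.5 and Table 10 give identical grades. With an assumed LLN of 90, a stable 80 mL/min is Grade 1 at baseline and Grade 0 on treatment. With an assumed LLN of 60, a stable 65 is ungraded at baseline and Grade 1 on treatment. Grades 2–4 have the same cut-points in both places.

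**The case against.** The strongest reply is that the table does what it says. Its output is titled as worst laboratory values, not treatment-emergent toxicity, the rule is disclosed, and it is an addition: the stated substitute for the shift tables is the PCS count, which does require worsening. Baseline clearance grades are tabulated for the safety population in the same strata, so a reader can set the two tables side by side. All of this stands, and it keeps the point small. It does not close the gap, because two marginal tables do not show how many patients moved, and hemoglobin has no baseline grades at all. The PCS limit on serum creatinine (above 132.605 µmol/L) may catch some patients with clearance of 50–74, but it counts creatinine, not clearance.

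Three stronger readings are tempting, and the documents do not support them.

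- *Real falls are hidden.* They are missed by the grade table and, above its limits, by the PCS count. They still enter the change-from-baseline summaries. Anemia is also covered by treatment-emergent adverse events, by ribavirin dose changes for anemia, and by transfusion and growth-factor use.
- *Baseline and on-treatment limits differ throughout.* Only the clearance Grade 0/1 boundary can differ, and only where a recorded LLN is not 75. The data lists in Protocol 9.4.1.1–9.4.1.3 request a reference limit only for ALT and AST (the ULN), and 9.6.1 restricts entry to protocol-specified data. The fallback of 75 may therefore be usual, although the mention of reference ranges in 9.7.4 means a recorded LLN cannot be excluded.
- *The cohort contains patients with kidney disease, dialysis or transplant.* SAP 4.2.6.4 lists summary categories. It does not show that such patients were enrolled.

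**Conclusion.** The point holds in a limited form. By explicit wording, on-treatment hemoglobin and creatinine-clearance grades include abnormality that was present before treatment. With the shift tables dropped, no baseline-referenced patient count remains for hemoglobin 80–129 g/L or clearance 50–74 mL/min. The visit-level change summaries limit the consequence but cannot say how many patients worsened.

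The size cannot be fixed from the documents, which give no hemoglobin or clearance distribution and no sex mix. The range of about 2 to 20 of 50–55 patients rests on the assumed means and SDs above and on one value per patient. The differing clearance limit at the Grade 0/1 boundary is a minor consistency point. This is a cheap improvement to a descriptive secondary safety output, and it does not touch the SVR12 analysis.

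**What to change.** In SAP 4.2.8.4, derive baseline grades for hemoglobin and creatinine clearance with the Table 10 limits. Cross-tabulate baseline grade against worst on-treatment grade in the safety population, overall and by regimen and cirrhosis status. Report the number and percentage whose grade worsened from baseline beside the existing worst-grade count. Use the fixed 75 mL/min limit for clearance at both times, so that no local LLN is needed, and align the baseline grading in SAP 4.2.6.5 with it.

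The cost is an SAP wording change and one table shell. The laboratory values are already collected, and no sex-specific or local lower limits are required. The downside is a larger table that will be sparse in 50–55 patients. The worsened count will still contain visit-to-visit noise (a move from 130 to 129 g/L counts). It will also miss falls within a grade (170 to 131 does not count), which is why the change-from-baseline summaries should stay.
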